f) Medical or scientific judgment should be exercised in deciding whether reporting is appropriate in other situations, such as important medical events that may not be immediately life-threatening or result in death or hospitalisation but may jeopardise the subject or may require medical or surgical intervention to prevent one of the other outcomes listed in the above definition. These should also be considered serious. Examples of such events are invasive or malignant cancers, intensive treatment in an emergency room or at home for allergic bronchospasm, blood dyscrasias or convulsions that do not result in hospitalisation, or development of drug dependency or drug abuse.

AE definitions

An AE is any untoward medical occurrence in a patient or clinical investigation subject or consumer, temporally associated with the use of a product, whether or not considered related to the product.

Examples of an AE include:

Exacerbation of a chronic or intermittent pre-existing condition including either an increase in frequency and/or intensity of the condition

New conditions detected or diagnosed after investigational product administration even though it may have been present prior to the start of the study

Signs, symptoms, or the clinical sequelae of a suspected interaction

Signs, symptoms, or the clinical sequelae of a suspected overdose

Examples of an AE do not include a/an:

Medical or surgical procedure (e.g., endoscopy, appendectomy); the condition that leads to the procedure is an AE

Situations where an untoward medical occurrence did not occur (social and/or convenience admission to a hospital)

Anticipated day-to-day fluctuations of pre-existing disease(s) or condition(s) present or detected at the start of the study that do not worsen

The disease/disorder being studied, or expected progression, signs, or symptoms of the disease/disorder being studied, unless more severe than expected for the subject's condition

All as per Brighton Collaboration where these definitions are available.

Definitions for local reactions and fever	
Local Reactions	Systemic Events

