
Level one diagnostic certainty is: Any description of morphological or physiological change at or near the injection site that is described or identified by a health care provider
 
Level two diagnostic certainty is: Any description of morphological or physiological change at or near the injection site that is described or identified by another person
 
Categories for event classification
 
Level 1: as specified in the case definition for a local reaction
 
Level 2: as specified in the case definition for local reaction
 
Insufficient evidence for a local reaction Not a case of a local reaction
 
Interval for onset of local reaction or first observation
 
>0-24 h 25-48 h 49-72h 73h – 7 days >7 days
 
Include numbers of subjects with local reactions newly present at each specified time as %.
 
Diameter of the local reaction
 
>0.0 - <1.0 cm ≥1.0 – 2.5 cm
	
Fever
 
Endogenous elevation of at least one measured body temperature of ≥38°C
 
Time intervals
 
0 – 24hr Day 1 0 – 24hr Day 2 Day 3-7...
 
Increments
 
<38°C 38.0-38.4°C 38.5-38.9°C Etc.... >41°C

≥2.5 – 5.0 cm ≥5.0 - <10.0 cm ≥10.0 - <15.0 cm ≥15.0 - <20.0cm ≥20.0 - <30.0 cm ≥30.0 cm
 
Pain scale to include measure of functionality
 
0 = No pain 1 = Mild, still able to move arm normally 2 = Moderate, hurts to move arm normally or to touch 3 = Severe, unable to move arm
	
--	--

Ethical considerations

Ethical approval for this study will be obtained from the NZ Ministry of Health and Disability Ethics Committee. These guidelines are based on statements from NZ and international guidelines, including the World Medical Association Declaration of Helsinki: Ethical principles for medical research involving human subjects (WMA 2008) and the Council for International Organizations of Medical Sciences' International Guidelines for Ethical Review of Epidemiological Studies (CIOMS 1991).

Details about the National Ethics Advisory Committee and the Ethical Guidelines for Observational Studies can be accessed <http://neac.health.govt.nz/streamlined-ethical-guidelines-health-and-disability-research>

Whilst we are not undertaking any clinical work (there is no intervention, only observation), we will be observing the standards required by the national ethics committee and GCP standards, in which our team are familiar.

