1c. Swelling	Is/was there any swelling either outside the hard woody lump or without any hard lump in the middle?								
	No swelling — go to next question	0							
	Yes, take measurement (measure tool used  OR estimate )	1	
 
 >0.0 – <1.0cm	2	
 
 =>1.0 – <2.5cm	3	
 
 =>2.5 – <5.0cm	4	
 
 =>5.0 – <10.0cm	5	
 
 =>10.0 – <15.0cm	6	
 
 =>15.0 – <20.0cm	7	
 
 =>20.0 – <30.0cm	8	
 
 =>30.0cm	9	
 
  1d. Pain intensity	Is/was there any pain where the injection was given?							
	No pain — go to next question	0							
	Yes, to what extent	1							
	• Mild, still able to move arm normally	2							
	• Moderate, hurts to move arm normally or to touch	3							
	• Severe, unable to move arm	4							
	1e. Interval and duration for onset of local event or first observation	Where applicable, how long after having the vaccination did the event occur? Circle as appropriate. How long did the event last?							
		Redness	Duratio n	Induratio n	Duratio n	Swelling	Duratio n	Pain	Durati on
		>0 – 24hrs	>0 – 24hrs	>0 – 24hrs	>0 – 24hrs	>0 – 24hrs	>0 – 24hrs	>0 – 24hrs	>0 – 24hrs
24 – 48hrs		24 – 48hrs	24 – 48hrs	24 – 48hrs	24 – 48hrs	24 – 48hrs	24 – 48hrs	24 – 48hrs	
49 – 72hrs		49 – 72hrs	49 – 72hrs	49 – 72hrs	49 – 72hrs	49 – 72hrs	49 – 72hrs	49 – 72hrs	
73hrs – 7 days		73hrs – 7 days	73hrs – 7 days	73hrs – 7 days	73hrs – 7 days	73hrs – 7 days	73hrs – 7 days	73hrs – 7 days	
>7 days			>7 days		>7 days		>7 days		

1. Did you feel feverish after you received the vaccine?		
	No fever — go to question 2c	0
	Yes, had fever	1
2a.	How long after the vaccine did the fever occur?	
	0–4 hrs	1
	5–8 hrs	2
	9–24 hrs	3
	or after 24 hrs?	4
2b.	Was the temperature measured?	
	Temperature not taken	0
	Temperature taken but don't know what it was	1
	Temperature taken and read as below:	
	<38°C	2
	38.0–38.4°C	3
	38.5–38.9°C	4
	39.0–39.4°C	5
	39.5–39.9°C	6
	40.0–40.4°C	7
40.5–41.0°C	8	
2c.	Was anti-fever/pain medicine given or did you take anti-fever/pain medicine? (e.g., panadol/nurofen)	
	No meds given/taken — go to question 3	0
	Yes, meds given/taken	1
	Don't recall	88
2d.	Was it given/taken before or after vaccination?	
	Before	1
	After	2
	Both	3
	Don't recall	88

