¹⁰Tavares et al Pregnancy and safety outcomes in women vaccinated with an AS03-adjuvanted split virion H1N1 (2009) pandemic influenza vaccine during pregnancy: A prospective cohort study. *Vaccine* 2011;29:6358

[figure not shown]

Figure: Percentage of subjects 19–64 years with solicited local and general symptoms during 15 days after vaccination

Fever = oral temperature $\geq 37.5^{\circ}\text{C}$ (99.5°F). Grade 3 referred to redness and swelling of diameter ≥ 50 mm; oral temperature $> 39.0^{\circ}\text{C}$ ($> 102.2^{\circ}\text{F}$); and for all other symptoms, prevented normal activity. From Weston et al, 2009.⁸

Study assessments and procedures

Scheduled assessments	Adverse events in mother	Outcomes for infant	Both mother and baby
At enrolment	
¹First contact with mother by phone (standard script, Appendix 2) as soon as possible after identification to
 
 • Provide information about study and obtain detailed informed consent for participation (written consent form sent out if verbal consent given by phone) • capture any solicited adverse events within first 48 hours and first 7 days of receiving vaccine (s) 
Contact GP once consent obtained to obtain details of vaccination (Appendix 3)
		
Contact with mother monthly either by phone or e-mail⁴. If infant has symptoms* consistent with pertussis or a significant contact** with proven case will be invited for clinical review by study team Paediatrician.
 
If an unsolicited adverse event is noted during these calls, it will follow the same safety reporting procedures as other AEs in the study.

4 weeks since vaccine administration	
²Written questionnaire (Appendix 5) to capture any solicited adverse events in mother up to 4 weeks after receipt of vaccine (s)
		
6-week check	
Written questionnaire (Appendix 6) administered by telephone to GP to
	
Written questionnaire (Appendix 6) administered by telephone to GP practice to
	

Pertussis in Pregnancy Safety (PIPS) Study Protocol
Confidential
Not for Public Circulation or Reproduction

	determine pregnancy outcome and medically attended adverse events in mother since last contact.	capture birth history, weight and head circumference, any congenital abnormalities, neonatal death (<29 days) Details of 6-week check and confirm receipt of 6-week vaccination. Document any prior GP or hospital visits.	

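### Survey 1 puts all fever onset after 24 hours into one code, so the protocol's Day 2 and Days 3–7 fever intervals cannot be filled

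*Protocol*

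**What the plan says.** The table of definitions for local reactions and fever, under AE definitions in the main protocol and again in Appendix 8, defines fever as "Endogenous elevation of at least one measured body temperature of ≥38°C". Beside it stand time intervals (the first 24 hours, the second day, then Days 3–7) and temperature increments starting with a below-38°C band. The line above the table reads "All as per Brighton Collaboration where these definitions are available". Study Two's Statistical Analyses section groups non-serious events by those definitions and presents the timing of onset after vaccination, with its distribution where appropriate.

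The data come from Appendix 6, Phone Survey 1. It asks "Did you feel feverish after you received the vaccine" and records a positive answer as having had fever. Item 2a then codes onset as 0–4 hours (1), 5–8 hours (2), 9–24 hours (3) or later than 24 hours (4). Item 2b accepts "Temperature not taken" (0), "Temperature taken but don't know what it was" (1), a reading below 38°C (2), and readings from 38.0°C upwards in bands (3 to 8). The negative answer is "No fever — go to question 2c", which bypasses items 2a and 2b.

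**The concern.** The form should supply the intervals that the protocol sets for showing fever. For local reactions the same form nearly does so, with separate onset bands for the first day, the second day, the third day and the rest of the first week. Fever onset has only one band after the first day.

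At stake is the onset distribution of one of the two reactions for which the protocol tabulates definitions. A scoring rule can be settled in an analysis plan, but information that was never recorded cannot be recovered there. The Canterbury question list in Appendix 8 refers fever timing to the table with the Day 1, Day 2 and Days 3–7 intervals, and joint analysis of maternal outcomes is foreseen. With Study Two coded as it is, a pooled fever-onset display could show only Day 1 against later.

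Two smaller faults sit in the same items. The label on the positive answer states more than the question asks. The skip also means that a reading of 38°C or more in a woman who did not feel feverish is never recorded, although the definition does not require her to feel feverish.

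**Working it through.** **Onset: protocol intervals against survey codes.**

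| Protocol interval for fever | Survey 1 item 2a | Can it be filled? |
|---|---|---|
| Day 1 (0–24 h) | codes 1 + 2 + 3 | yes, by adding |
| Day 2 (24–48 h) | code 4, shared | no |
| Days 3–7 | code 4, shared | no |

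The local-reaction onset grid in the same form has bands of 0–24 h, 24–48 h, 49–72 h and 73 h–7 days, so the three intervals could have been recorded.

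**What the merged code leaves unknown.** Let k be the number of women with defined fever and onset code 4, and let d of them have onset on Day 2. The form gives k but not d, and d can be any whole number from 0 to k. Out of 300 women, the Day 2 rate lies in [0, k/300] and the Days 3–7 rate is (k − d)/300. The uncertainty has width k/300 for each interval and does not shrink with more careful analysis.

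**Scale, using the protocol's own intervals.** The protocol gives no fever rate. Its only relevant figures are the 95% confidence intervals for an event proportion with 300 women. Exact (Clopper–Pearson) limits reproduce them:

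- 30/300 = 10%: 6.85–13.97% (protocol 7–14%)
- 15/300 = 5%: 2.83–8.11% (protocol 2.8–8.1%)
- 3/300 = 1%: 0.21–2.89% (protocol 0.2–2.9%)

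Purely as an illustration, take k = 15. The Day 2 rate could be 15/300 = 5.0% (2.8–8.1%) or 0/300 = 0%, with upper limit 1 − 0.025^(1/300) = 1.2%. The same completed forms are compatible with both. With k = 3 the range is 0 to 1.0%. Neither k is a forecast.

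**Case status: what item 2b already separates.**

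| Item 2b code | Meaning | Against the definition |
|---|---|---|
| 3 to 8 | reading of 38.0°C or more | case |
| 2 | reading below 38°C | not a case |
| 1 | reading taken, value unknown | unverified, countable |
| 0 | no reading taken | unverified, countable |
| not asked | did not feel feverish | any reading is lost |

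Among women who felt feverish, the form therefore identifies defined fever and counts those without usable evidence. The table of definitions gives local reactions a class for this ("Insufficient evidence for a local reaction") but gives fever none. Only the last row is information that the form never collects.

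**The case against.** The strongest reply is that the protocol does state how fever is scored. Events are to be grouped by Brighton definitions, the table gives a measured threshold, and the felt-feverish question is a screening question ahead of item 2b. That stands. A reader might infer that fever has no stated definition, that the rate depends on an unstated choice of rule, or that unmeasured women cannot be handled. The documents support none of these: nothing says the positive screening answer will be reported as the fever rate, and item 2b makes unmeasured women visible. How they are tabulated is ordinary analysis-plan detail.

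The day bands are also reporting strata rather than part of the case definition, so merging them does not change who counts as a case. That is correct, and it limits the point to the onset distribution.

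It can further be said that Survey 1 opens by asking about the first 48 hours, which would make the late code mean Day 2 alone. But the Study Two procedures also call for events in the first 7 days, and the local-reaction bands in the same form run to 7 days. If the 48-hour wording did govern, Days 3–7 would not be collected at all, and the intervals would still be unfilled. Survey 2 offers partial relief at best: its general adverse-event question has a start date, but it has no fever item.

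Finally, a reader might see a rival definition in the legend beginning "Fever = oral temperature" in Appendix 8, which uses 37.5°C. That legend describes a cited study of people aged 19–64. The survey's below-38°C box matches the protocol's own first increment, and no comparison at 37.5°C is planned.

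**Conclusion.** The point holds as a mismatch between the protocol's fever intervals and the form that feeds them. Day 2 and Days 3–7 cannot be separated, and this cannot be repaired after collection. The label on the positive answer and the skip past the temperature item are lesser faults on the same page.

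The consequence is modest: one descriptive solicited-event rate and its onset distribution in about 300 women. No sample size or hypothesis test depends on it. The uncertainty for each late interval is k/300, which follows from the form alone. A reader might go on to infer that the survey overstates fever by some particular amount. The documents give neither the share of women who feel feverish nor the shares with a reading or with a reading of 38°C or more, so any such figure would rest wholly on assumption. None is offered here as evidence.

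**What to change.** In Appendix 6, Phone Survey 1:

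- Replace the late-onset code in item 2a with 24–48 h and Days 3–7. The later band may be split at 72 h, as for local reactions.
- Relabel the positive answer to the opening question as felt feverish.
- Ask item 2b of all women, so that a reading is not lost when a woman did not feel feverish.

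In the analysis, count defined fever only from item 2b codes 3 and above, and show felt-feverish women with no reading or an unknown reading as a separate row.

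The cost is a few changes to the form and its code table, with one more short question for women who did not feel feverish. No extra contact or equipment is needed. For women already interviewed on the present codes, onset should be shown as Day 1 against later, with a note saying why.

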Appendix 1: Study Two Eligibility Criteria

PIPS (Pertussis in Pregnancy Safety) Study

Eligibility form for pregnant woman receiving Tdap vaccine at your practice

Inclusion criteria	
1. Is the patient a pregnant woman who has just received the Tdap vaccine during pregnancy between 28 and 38 weeks of gestation?	 Yes  No
2. Is the patient compliant with routine antenatal care, including at least one ultrasound early in pregnancy?	 Yes  No
3. Does your practice have the associated information on the specific vaccines given, including batch number?	 Yes  No

If the answers to **all** the inclusion criteria are ‘**yes**’, please give the potential participant a Patient Participant Information Sheet Summary to read and follow up with the Referral Form.

If the patient is happy to have their contact details passed on to the study team, please make sure they are given a copy of the full Patient Participant Information Sheet and the measuring strip before they leave the practice.

APPROVED BY THE UNIVERSITY OF AUCKLAND HUMAN PARTICIPANT ETHICS COMMITTEE ON **/**/** for *** years. Ref No ****/****

Appendix 3: Study Two Referral Form

**PIPS (Pertussis
in Pregnancy
Safety) Study
Referral Form**

Practice name:	
Form completed by:	
Date form completed:	
Date vaccination given:	
Vaccine product:	
Vaccine batch number:	
Patient's name:	
Patient's NHI number:	
Patient's date of birth:	
Patient's ethnicity:	
Patient's home phone no:	
cell phone no:	
Estimated due date:	

If the patient **DOES NOT** consent to be contacted, please complete the **italicised** information above only, provide a reason for declining (**see bottom of form**) and return this form to the research team.

1. Arm in which vaccine was given?	 Left	 Right
2. Was there any immediate reaction (within 30mins)?	 Yes (please describe reaction)	 No
3. Were concomitant vaccines given?	 Yes (what other vaccines?)	 No
4. Has the patient had a previous pertussis booster?	 Yes (please provide product name and batch if available) Product..... Batch no.....	 No
5. Does the patient have a history of fever or vaccination reaction?	 Yes (please provide details)	 No
6. Does the patient have any underlying health or medical conditions?	 Yes (please list conditions)	 No

If the patient chooses **NOT** to be contacted about this study, please ask why and select the option below that best

Pertussis in Pregnancy Safety (PIPS) Study Protocol
Confidential
Not for Public Circulation or Reproduction

describes their answer:			
	Too busy		Unable to be contacted
	Dislike being involved in research		Little or no English
	Other (please state):		

Thank you for your time. If you have any questions about this form, please feel welcome to call the Principal Investigator [name] on [name] or the Project Manager [name] [name].

Fax: Attention [name] IMAC Research [name]

Scan and email: [contact]

Appendix 6: Study Two Phone Survey 1 (48hrs–7days post vaccine)

[name]
 Department of General Practice & Primary Health
 SCHOOL OF POPULATION HEALTH
 The University of Auckland
 [name]
 Auckland, 1142
 [contact]

PIPS Study Patient Participant Phone Interview 1 (48 hours–7days post vaccine)

The following questions ask about your memory of events for the period immediately (within 48 hours) following when you received the dose of Tdap vaccine (whooping cough vaccine).

Since having the vaccine, have you experienced any of the following at the place on your arm where you had the injection?

[Tease out potential symptoms and events related to vaccination eg, distinguish between what may be related to pre/post-pregnancy, “is this more than usual?”]

If you have had any redness or swelling, use the clear plastic measure the practice nurse gave you.

Use the smallest circle you can use to cover all of the redness or swelling, and this will give you the measurement of the reaction. If the reaction is bigger than the biggest circle, use the ruler down the side.

Event	Description/Question	Grade/Response	
1a. Redness	Has there been any redness where the injection was given?		
	No redness — go to next question	0	
	Yes, take measurement (measure tool used  OR estimate )	1	
 
 >0.0 – <1.0cm	2	
 
 =>1.0 – <2.5cm	3	
 
 =>2.5 – <5.0cm	4	
 
 =>5.0 – <10.0cm	5	
 
 =>10.0 – <15.0cm	6	
 
 =>15.0 – <20.0cm	7	
 
 =>20.0 – <30.0cm	8	
 
 =>30.0cm	9	
 
  1b. Induration	Is/was there a hard, woody lump with defined edges, where the injection was given?	
	No induration — go to next question	0	
	Yes, take measurement (measure tool used  OR estimate )	1	
  
 
 
 
© Immunisation Advisory Centre, The University of Auckland_V2_29/10/2013
		

	>0.0 – <1.0cm	2							
	=>1.0 – <2.5cm	3							
	=>2.5 – <5.0cm	4							
	=>5.0 – <10.0cm	5							
	=>10.0 – <15.0cm	6							
	=>15.0 – <20.0cm	7							
	=>20.0 – <30.0cm	8							
	=>30.0cm	9							
1c. Swelling	Is/was there any swelling either outside the hard woody lump or without any hard lump in the middle?								
	No swelling — go to next question	0							
	Yes, take measurement (measure tool used  OR estimate )	1	
 
 >0.0 – <1.0cm	2	
 
 =>1.0 – <2.5cm	3	
 
 =>2.5 – <5.0cm	4	
 
 =>5.0 – <10.0cm	5	
 
 =>10.0 – <15.0cm	6	
 
 =>15.0 – <20.0cm	7	
 
 =>20.0 – <30.0cm	8	
 
 =>30.0cm	9	
 
  1d. Pain intensity	Is/was there any pain where the injection was given?							
	No pain — go to next question	0							
	Yes, to what extent	1							
	• Mild, still able to move arm normally	2							
	• Moderate, hurts to move arm normally or to touch	3							
	• Severe, unable to move arm	4							
	1e. Interval and duration for onset of local event or first observation	Where applicable, how long after having the vaccination did the event occur? Circle as appropriate. How long did the event last?							
		Redness	Duratio n	Induratio n	Duratio n	Swelling	Duratio n	Pain	Durati on
		>0 – 24hrs	>0 – 24hrs	>0 – 24hrs	>0 – 24hrs	>0 – 24hrs	>0 – 24hrs	>0 – 24hrs	>0 – 24hrs
24 – 48hrs		24 – 48hrs	24 – 48hrs	24 – 48hrs	24 – 48hrs	24 – 48hrs	24 – 48hrs	24 – 48hrs	
49 – 72hrs		49 – 72hrs	49 – 72hrs	49 – 72hrs	49 – 72hrs	49 – 72hrs	49 – 72hrs	49 – 72hrs	
73hrs – 7 days		73hrs – 7 days	73hrs – 7 days	73hrs – 7 days	73hrs – 7 days	73hrs – 7 days	73hrs – 7 days	73hrs – 7 days	
>7 days			>7 days		>7 days		>7 days		

1. Did you feel feverish after you received the vaccine?		
	No fever — go to question 2c	0
	Yes, had fever	1
2a.	How long after the vaccine did the fever occur?	
	0–4 hrs	1
	5–8 hrs	2
	9–24 hrs	3
	or after 24 hrs?	4
2b.	Was the temperature measured?	
	Temperature not taken	0
	Temperature taken but don't know what it was	1
	Temperature taken and read as below:	
	<38°C	2
	38.0–38.4°C	3
	38.5–38.9°C	4
	39.0–39.4°C	5
	39.5–39.9°C	6
	40.0–40.4°C	7
40.5–41.0°C	8	
2c.	Was anti-fever/pain medicine given or did you take anti-fever/pain medicine? (e.g., panadol/nurofen)	
	No meds given/taken — go to question 3	0
	Yes, meds given/taken	1
	Don't recall	88
2d.	Was it given/taken before or after vaccination?	
	Before	1
	After	2
	Both	3
	Don't recall	88
2. Did you have any other symptoms after you received the vaccine?		

No — go to question 4	0
Yes — circle below as appropriate	1
Events	
Nausea, vomiting or diarrhoea	1
Headache	2
Fatigue, lethargy or general weakness	3
Events around the area where you got the injection (other than those already discussed)	4
Pain (including muscle or joint pain: not injection site pain)	5
Intense shivering/Shaking	6
Other (details)	7
3. Did you need to see or call the doctor for any reason in the 24–48 hours after having the vaccine?	
No, did not need to contact the doctor — go to question 5	0
Yes, did need to contact the doctor	1
Who did you see?	
Where?	
For what reason?	
Can we contact your doctor for more information?	Yes / No
4. Other than the vaccine you just had, have you received the Tdap (Boostrix®) vaccine (whooping cough) previously?	
No, not had Tdap before — go to end	0
Yes, had Tdap before (may need prompt, eg, if they have had tetanus in recent years)	1
Don't know — go to end	88
Can you remember which brand it was? What brand was it?	Yes / No

Ethical approval

APPROVED BY THE UNIVERSITY OF AUCKLAND HUMAN PARTICIPANT ETHICS
COMMITTEE ON **/**/** for *** years. Ref No ****/**.

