- National Maternity Collection.

Data cleansing and data matching will progress for the first half of 2014.

Analysis will be carried out during the second half of 2014.

Study Two (intensive monitoring study of pregnant women)

Year 1: 2013

Enrolment

Practice staff will identify potential participants based on eligibility criteria (*Appendix 1*), provide them with an information sheet summary (*Appendix 2*) and with their consent, complete and fax a referral form (*Appendix 3*) to the research team. Practice staff will provide women consenting to be contacted by the research team with a full participant information sheet (PIS) (*Appendix 5*) to take home. A member of the research team will make the first contact with mother by phone as soon as possible after identification to:

provide further information about study and obtain verbal informed consent for participation (written consent form sent out following verbal consent given by phone, *Appendix 4*)

capture any solicited events within first 48 hours and first 7 days of receiving vaccine(s)¹⁰ (*Appendix 6*).

Contact General Practice once consent obtained for cross checking recorded DOB, ethnicity, NHI, due date and vaccination history details.

Four weeks post-vaccine administration to pregnant woman (prospective)

Phone interview (*Appendix 7*) to capture any solicited events in mother up to four weeks after receipt of vaccine. Any events requiring General Practice consultation will be verified by the practice.

End of data collection: Provide voucher to mother to acknowledge time contribution.

Canterbury DHB – additional data.

(See Canterbury DHB study protocol for additional data on infant outcomes [*Appendix 8*])

Informed consent:

An additional consent form (included in *Appendix 8*) will be used to obtain signed informed consent for participation and handling of personally identifiable information and safety data.

¹⁰For cases contacted retrospectively we will rely on patient recall of events.

If a woman chooses not to participate or to withdraw from the study at a later date the reason for non-participation or withdrawal will be recorded when given.

Confidentiality:

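### Survey 1 in Study Two sets a 48-hour recall period against a stated 7-day window, so solicited capture of local reactions and fever on days 3–7 depends on when the call is made

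*Protocol*

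**What the plan says.** **Window assigned to the call.** Protocol, Study procedures, Study Two, Enrolment: "A member of the research team will make the first contact with mother by phone as soon as possible after identification to" give information, obtain consent and "capture any solicited events within first 48 hours and first 7 days of receiving vaccine(s". No earliest day is set there. The title of the Appendix 6 form gives a slot from 48 hours to 7 days after vaccination.

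**Recall period on the form.** The lead-in of Appendix 6 says its questions "ask about your memory of events for the period immediately (within 48 hours) following when you received the dose of Tdap vaccine". The local-reaction question that follows has no upper limit: "Since having the vaccine, have you experienced any of the following at the place on your arm where you had the injection". The fever and other-symptom questions are equally open. Item 1e offers local-reaction onset codes up to 73 hours–7 days and duration codes up to more than 7 days. The last fever-onset code is "or after 24 hrs". The doctor-contact item reads: "Did you need to see or call the doctor for any reason in the 24–48 hours after having the vaccine".

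**Intervals wanted.** The table of definitions for local reactions and fever, under AE definitions, lists local-reaction onset intervals to 73 hours–7 days and beyond, and instructs: "Include numbers of subjects with local reactions newly present at each specified time as" a percentage. For fever it lists Day 1, Day 2 and Day 3–7.

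**Later contact.** Appendix 7 (Survey 2, at 4 weeks) asks whether any adverse event or symptom occurred in the month, with start and resolution dates, and whether a doctor was needed for any reason since vaccination. Its itemised list includes no redness, induration, swelling, injection-site pain or fever.

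**The concern.** Rates and patterns of adverse events in vaccinated women are the safety endpoint of Study Two, and its Statistical Analyses section promises the timing of events relative to vaccination. The form that supplies local reactions and fever gives the interviewer two recall periods on one page, and the call may come before most of the 7-day window has passed.

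A woman called at 48 hours cannot report an onset on days 3–7, whatever the wording. A reaction still present when she is called has its duration cut short, and item 1e has no code for a reaction that is continuing. A woman called on day 5 may be held to 48 hours by the lead-in or asked about all five days by the question itself, depending on the interviewer.

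The percentages by onset interval would then mix women observed for different lengths of time. The error runs one way: late reactions are under-counted and the later intervals look safer than they are. This matters too because the protocol intends Study Two maternal data to be directly comparable, and analysed jointly, with Study Three, whose own protocol (Appendix 8) uses the same interval definitions.

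**Working it through.** No sample-size or power figure in the protocol depends on this point. The check compares the windows and then does simple arithmetic.

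**1. Windows compared**

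| Source | Window |
|---|---|
| Enrolment procedure | first 48 hours and first 7 days |
| Appendix 6, title | call between 48 hours and 7 days |
| Appendix 6, lead-in | within 48 hours |
| Appendix 6, local-reaction and fever questions | vaccination to the call |
| Appendix 6, item 1e | onset to 7 days; duration to more than 7 days |
| Appendix 6, doctor-contact item | hours 24 to 48 |
| Definitions table, fever | Day 1, Day 2, Day 3–7 |
| Appendix 6, last fever code | any time after 24 hours |

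The lead-in and the doctor-contact item do not fit the other rows, and the last fever code is coarser than the definitions table.

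**2. Days not yet observed at the first call**

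For a call on day d, unobserved days = 7 − d.

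| Call day | 2 | 3 | 4 | 5 | 6 | 7 |
|---|---|---|---|---|---|---|
| Days unobserved | 5 | 4 | 3 | 2 | 1 | 0 |
| Share of 7 days | 71% | 57% | 43% | 29% | 14% | 0% |

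The protocol gives no call-date distribution, so the range is 0 to 5 days. If calls were spread evenly over days 2 to 7 (an assumption), the mean would be 15/6 = 2.5 days, or 2.5/7 = 36%.

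**3. What this could do to a rate (illustration)**

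Let q be the true proportion with onset on days 3–7 and f the share of women called at 48 hours, with the rest called at day 7. The protocol gives neither. If Survey 2 recovers nothing, the recorded rate is q × (1 − f).

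| f | 0 | 25% | 50% | 75% | 100% |
|---|---|---|---|---|---|
| q = 5% | 5.0% | 3.75% | 2.5% | 1.25% | 0% |
| q = 1% | 1.0% | 0.75% | 0.5% | 0.25% | 0% |

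If Survey 2's general question recovers a share r of the missed events, the recorded rate is q × (1 − f × (1 − r)). With q = 5%, f = 50% and r = 50% it is 5% × 0.75 = 3.75%.

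For scale, the protocol gives a 95% interval of 2.8–8.1% for an event seen in 5% of 300 women. The exact interval for 15/300 reproduces it. The lower limit is 2.2 points below 5%. With f = 50% and r = 0 the shift is 2.5 points, so under those assumptions the bias is as large as the stated sampling error.

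**4. Fever code**

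At a call made at 48 hours, an onset after 24 hours can only be Day 2. At any later call the same code can mean Day 2 or Day 3–7, and the form offers no code to tell them apart.

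**The case against.** The strongest case is that only the lead-in sentence limits recall. The questions themselves are open, item 1e has codes to 7 days and beyond, and a woman called near day 7 is asked about the whole week. A referral must be faxed before the team can call, which makes a 48-hour call the extreme case, and a footnote foresees later calls that rely on recall. Survey 2 asks about any adverse event in the month with dates, and about any doctor visit since vaccination; visits to General Practice are verified with the practice. Interval-specific denominators can be left to a SAP.

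Much of this stands. A reader might infer that the first interview covers only 48 hours and that days 3–7 are never solicited. The open questions and the 7-day codes do not support that. Nor do they support saying that late fever cannot be dated for any participant: a 48-hour call leaves only Day 2, and a start date given at 4 weeks would settle other cases. The doctor-contact gap is largely backed up by Survey 2. No text fixes the denominator at all women, and no fever timing table is promised.

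What does not fall away is the contradiction in recall period and the lack of any itemised question on local reactions or fever after an early call. A general question at 4 weeks is a weaker prompt and does not grade size, pain or temperature.

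**Conclusion.** The point holds as a conflict between passages whose effect depends on the call date. The 48-hour lead-in and the 24–48-hour doctor-contact item contradict the 7-day window in the enrolment procedure, and the lead-in also contradicts the form's own codes. With the call made as soon as possible from 48 hours and not repeated near day 7, between 0 and 5 of the 7 days are unobserved at the first call. Local reactions and fever on days 3–7, and durations running past the call, are likely to be under-counted, though not wholly missed.

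A reader might take 71% as the share of reactions lost. It is the share of days not yet observed when the call falls on day 2. The loss in events depends on when reactions begin, on the call dates and on what Survey 2 recovers, none of which the protocol gives. The 36% average rests on an assumed even spread of calls. The fever-code limitation applies to women called after day 2 and needs no assumption about rates.

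**What to change.** Reconcile the enrolment procedure, the definitions table and Appendices 6 and 7 as follows:

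- Change the Appendix 6 lead-in to ask about the time from vaccination up to today (to day 7).
- Record the call date on Survey 1, so that each woman's observed time is known. Appendix 7 has a date field; none is visible on Appendix 6.
- Repeat the local-reaction and fever items in the existing 4-week call, asking about anything new or still present since the first call.
- Reword the doctor-contact item to cover the whole time since vaccination.
- Split the last fever-onset code into 25–48 hours, days 3–7 and more than 7 days.

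The cost is rewording two questionnaires, about two extra minutes in a call already planned, and somewhat longer recall for the repeated items. Moving the first call to day 7 would also close the gap, but it lengthens recall of the first 48 hours. Repeating the items at 4 weeks leaves the early call in place.
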